injection of Exparel can provide adequate pain relief over 3 days it can make obsolete the need to place a continuous nerve block catheter. There are significant benefits to this. It requires more skill and time to place a catheter versus a single injection of a local anesthetic for a TAP block. Other benefits are related to the avoidance of catheter maintenance including dressings, leakage at catheter insertion site, and the need for additional infusion pumps. Furthermore, any catheter has the possibility of infection or bleeding.

It is the purpose of this study to evaluate the efficacy of methods that allow for continuous release of local anesthetic in the TAP space, either via catheter or via injecting Exparel® a slow release liposomal space versus the standard single injection Bupivacaine in the TAP space. The study shall consist of three (3) arms of which patients will be randomly assigned: Continuous TAP block (CTAP) via Catheter, Single Injection TAP block with the slow release liposomal Exparel, and Single Injection TAP block with Bupivacaine. Several parameters will be measured with the primary goal being to determine the effectiveness and duration of post-operative pain relief.^{8,9}

Primary Hypothesis

Methods that allow for continuous release of local anesthetic in the TAP space will decrease total narcotic requirements vs. the standard single shot Bupivacaine control. A continuous release of local anesthetic in the TAP space via catheters over 2 days will result in lower total narcotic requirements when compared to the single shot Bupivacaine injection technique when measured over 48 hrs. The Liposomal agent Exparel® which releases the Bupivacaine local anesthetic over three days should also allow for a single injection technique that can provide similar post-operative pain response to that of the catheter method without the need to place a catheter in the TAP space. Post-operative narcotic requirements are inversely related to post-operative pain control and patient satisfaction and total narcotic requirements will be significantly higher in the single shot group vs. the continuous release groups over 48 hrs.

Purpose of the Study Protocol

The purpose of this study protocol is to ensure consistent implementation of this study across all study sites.

B Background

Prior Literature and Studies

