The analgesic efficacy of the TAP block has been demonstrated in prospective randomized trials compared with placebo, in several surgical procedures such as abdominal surgery³, hysterectomy², retro-pubic prostatectomy¹, Caesarean section⁷, laparoscopic cholecystectomy⁵, and appendectomy⁶. These studies reported superiority of the TAP block in terms of reduction in visual analogue scale scores and narcotic consumption. In two of the studies, the authors suggest the decrease in morphine consumption lasted for 2 days⁴. However, this difference was established during the first 24 hr. and remained stable thereafter. Therefore, we can assume the analgesic effect of the TAP block persists for at least 24 hr. and the TAP block should be

considered an integral part of a multimodal analgesic strategy including systemic analgesic agents to control residual pain. The fact that the TAP block may contribute to decreasing the incidence of narcotic side effects such as nausea and vomiting is also beneficial to the patient's rehabilitation.

Rao Kadam, et al., compared epidural to continuous TAP block, Epidural versus continuous transversus abdominis plane catheter technique for postoperative analgesia after abdominal surgery¹⁰, finding no significant difference in terms of post-operative narcotic requirements. Although the study was underpowered, given the accepted and well-studied use of thoracic epidural for controlling post-operative pain, this is highly suggestive of the Continuous TAP block's efficacy for controlling post-operative pain.

Petersen, et al., demonstrated the spread of the TAP sensory block is also partly maintained by a continuous 24 hour Ropivacaine infusion via a TAP catheter versus a placebo *infusion, transversus abdominis plane (TAP) block with 24 hours Ropivacaine infusion via TAP catheters: A randomized trial in healthy volunteers*⁷.

Xan Jacobs, et al., conducted a Retrospective Review of Exparel® in Infiltration-transversus Abdominis Plane (i-TAP) Blocks in Hand-assisted Nephrectomy and Colorectal Procedures¹¹. These findings suggest that that the use of Exparel® in i-TAP blocks is a useful adjunct to postoperative pain control up to 72 hours post-injection in those patients undergoing hand-assisted abdominal procedures. This study also suggests a favorable safety profile with no adverse events related to the use of Exparel in an infiltrative TAP block.

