
Furthermore, our expectation is that this difference will be most apparent at 48 hrs. as discussed above with a reduction in narcotic requirements greater than 40% in the continuous catheter TAP group vs. standard single shot Bupivacaine TAP (4.1 mg +/- 3 mg vs. 2.4 mg +/- 1.3 mg Dilaudid). This is based on the assumption that the effects of the local anesthetic control TAP (single shot Bupivacaine) may last up to 24 hrs. At 72 hrs, prior studies, although limited, have not shown a significant difference between TAP block and placebo groups.

c Study Objectives

Primary Aim

The primary aim is to evaluate for any significant difference total post-operative narcotic requirements (Dilaudid) required over 48 hrs. in the continuous catheter TAP block arm vs. the single shot Bupivacaine TAP arm and again the slow release Liposomal Exparel® TAP arm vs. the single shot Bupivacaine TAP arm.

Secondary Aim

The secondary aim will be to evaluate for any significant difference in narcotic requirements at other endpoints such as 24 hrs and at 72 hrs. As discussed before, current studies do not show a significant difference when extrapolated out at those end points, albeit there is very little data at 72 hrs. Other quality indicators of recovery in the three arms such as Visual Analog Scores (VAS) are expected again to be most significantly different at 48 hrs. Other quality measures that will be recorded include incidence and severity of post-operative nausea and vomiting (PONV), time to ambulation, and patient satisfaction with post-operative pain control.

Rationale for the Selection of Outcome Measures

Outcome measurements are based on the assumption that narcotic requirements (i.e. intravenous Dilaudid Patient-Controlled Analgesia [PCA] use) are inversely related to patient satisfaction in regards to their post-operative pain. Additional factors such as VAS, ambulation, performance of daily activities, and anti-emetic pharmaceutical requirements have been chosen as quality indicators in regards to post-operative pain control and dependence on narcotics.

D Investigational Agent

This investigation will use three FDA-approved techniques:

- Bilateral Continuous TAP block via Catheter (One-time bolus of Bupivacaine 0.25% x 20ml per side followed by continuous infusion of Ropivacaine 0.2% 7 ml/hr. per side x 48 hrs.);
- Single Injection TAP block with Exparel® (One-time bolus of Bupivacaine 0.25% x 20 ml followed by Exparel 133 mg per side); and

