- Single Injection TAP block with Bupivacaine 0.25% (25 ml-30 ml volume one-time bolus per side).

E Study Design

Overview or Design Summary

It is the purpose of this study to evaluate the efficacy of continuous TAP block via catheter versus single shot Bupivacaine TAP block and also to evaluate the efficacy of slow release Exparel® versus single shot Bupivacaine. The study shall consist of three (3) arms of which patients will be randomly assigned: Bilateral Continuous TAP block via Catheter (One time bolus of Bupivacaine 0.25% x 20 ml per side followed by continuous infusion of Ropivacaine 0.2% 7 ml/hr. per side x 48 hrs); Single Injection TAP block with Exparel® (One time bolus of Bupivacaine 0.25% x 20 ml followed by Exparel 133 mg per side); and Single Injection TAP block with Bupivacaine 0.25% (25-30 ml volume one time bolus per side). Several parameters will be measured with the primary goal being to determine the effectiveness and duration of post-operative pain relief of the newer techniques of extending TAP block duration with the current, commonly used standard single shot Bupivacaine technique. Because a goal of this study is to determine which technique of TAP block is most effective for post-operative pain control, the three (3) arms of this study will be performed in a manner that is most consistent and common with current anesthesia practice. Because TAP block is typically most effective for lower and mid-abdominal incisional pain relief, the nature and height of the incision with regard to the umbilicus will also be recorded.

Parameters Measured:

- 1) Total Post-operative Narcotic Requirements over at 24, 48 and 72hrs.
- 2) Days of IV PCA use: Time to 1st dose, total IV PCA requirements, POD# 0, 1, 2, & 3, additional narcotic use and additional adjuvants
- 3) PACU narcotic requirements
- 4) Pain Score:0-10 on post-operative day (POD)# 0, POD #1, POD #2, POD #3 (am, pm, Max Pain score per day, Pain score at rest, and Pain score with activity)
- 5) Day to Ambulation: O=out of bed assisted/unassisted, W= walk with/without assistance

- 6) Day of Foley removal
- 7) Day of first Bowel Movement
- 8) Anti-emetic Drug (Zofran) requirements.
- 9) Surgical Incisional height in relation to umbilicus or Type of Surgery (recorded by anesthesiologist)
- 10) Anesthesia provider placing TAP block
- 11) Patient weight/BMI
- 12) Day of discharge

Subject Selection and Withdrawal

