F3.d Data Collection Procedures for Adverse Events

Please see Attachment L2 for data collection form. All adverse event data will be entered into Oncore ERM.

F3.e Reporting Procedures

Serious Adverse Events and adverse events that meet "severe" criteria must be directly reported within 24 hours to the Principal Investigator, and the IRB.

[name] M.D.
[contact]
[contact]
Department of Anesthesiology
Midwestern Regional Medical Center
Zion, IL

Other adverse events must be entered within 7 days of collection into the Oncore ERM.

F3.f Post-study Adverse Event

Serious Adverse Events and adverse events that meet "severe" criteria must be directly reported within 24 hours to, the Principal Investigator and the IRB.

[name] M.D.
[contact]

[contact]
Department of Anesthesiology
Midwestern Regional Medical Center
Zion, IL

Other adverse events must be entered within 7 days of collection into the Oncore ERM.

F3 Study Outcome Measurements and Ascertainment

G Statistical Plan

Interim Monitoring and Early Stopping

The Principal Investigator will utilize the Oncore ERM study management system to monitor the study.

The study may be stopped early for the following reasons:

- withdrawal of funding
- safety issues
- drug has been proven effective and no further testing is needed

Analysis Plan

The study is a prospective, randomized, open, active controlled clinical trial. Effectiveness of the Continuous TAP (CTAP) via the ON-Q[®] Pain Management System will be evaluated and compared to single shot techniques with respect to reductions in postoperative opioid consumption over the first 72 hours postoperatively. Secondary outcomes including hospital length of stay (LOS), time in PACU, pain at rest and with activity, return of bowel function, and incidence of opioid related side effects will also be evaluated.

The aims of this study are to compare the efficacy of continuous TAP block via ON-Q[®] system versus that of single injection techniques for TAP block regarding opioid reduction among patients undergoing major abdominal surgery. It is hypothesized that a continuous TAP block technique reduces pain, the need for opioids as well as the expected length of stay relative to those resulting from those subjects receiving a single TAP injection of Exparel (liposomal Bupivacaine) or single TAP injection of Ropivacaine to treat postoperative pain.

Study success criteria:

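### Duration of relief is part of the primary goal, but the opioid outcomes are running totals and no interval contrast is planned as the evidence on duration

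*Combined protocol and SAP*

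**What the plan says.** The Study Abstract and the design summary in section E both describe "the primary goal being to determine the effectiveness and duration of post-operative pain relief". The Rationale adds that the extra cost of the continuous-release methods, and for catheters the skill and upkeep, should be repaid by significantly longer relief. It takes single-shot bupivacaine to act for up to 24 h.

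The opioid outcomes are these:

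- Primary Aim (section C): "total post-operative narcotic requirements (Dilaudid) required over 48 hrs".
- Secondary Aim (section C): "any significant difference in narcotic requirements at other endpoints such as 24 hrs and at 72 hrs".
- Parameters Measured (section E), item 1: "Total Post-operative Narcotic Requirements over at 24, 48 and 72hrs".
- Analysis Plan (section G): "reductions in postoperative opioid consumption over the first 72 hours postoperatively".

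The Statistical Analysis Plan in section G compares mean opioid consumption between arms. It attaches no time window to that comparison and names no interval, per-day contrast or longitudinal model.

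The protocol does collect time-resolved data. Parameters Measured lists time to first PCA dose, PCA use on POD 0 to 3 and pain scores on POD 0 to 3. The data form in section L has a row for each opioid, with columns for PACU and POD 0 to 3. Pain at rest and with activity is a named secondary outcome in section G.

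**The concern.** The trial's premise concerns timing: all arms receive bupivacaine at the start, and the continuous-release arms should separate from single shot once that block wears off. A running total does not locate a difference in time. A benefit gained entirely on day 1 would appear in the 24, 48 and 72 h totals alike.

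The protocol's own background shows why this matters. Of the 2-day opioid reduction reported in earlier studies it says that "this difference was established during the first 24 hr. and remained stable thereafter", and it then assumes an analgesic effect of at least 24 h only. A lower 48 h or 72 h total here would invite the same remark. What is at stake is any statement that a catheter or liposomal bupivacaine prolongs relief beyond a single shot. Choosing intervals after the results are known, in a trial whose plan says it is not blinded, would carry much less weight than naming them now.

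**Working it through.** **1. The plan's own figure.** Inputs from Sample Size (section G): means 4.1 and 2.4 mg, SD 3 mg in both arms, two-sided 0.05, 80% power.

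n = 2 × SD² × (1.960 + 0.842)² / difference² = 2 × 9 × 7.849 / 1.7² = 48.9, so 49 per arm. This reproduces the stated 49 (a noncentral-t calculation gives 50). With 53 recruited per arm and 10% dropout, 53 × 0.9 = 47.7, so about 48 are evaluable.

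**2. Carry-over.** For each patient, 72 h total = 48 h total + use in hours 48–72. The between-arm differences add in the same way:

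D72 = D48 + D(48–72)

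If D48 = 1.7 mg and D(48–72) = 0, then D72 = 1.7 mg. The same identity links the 24 h and 48 h totals.

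**3. How often the 72 h total would be significant with no day-3 difference.** The documents give neither the SD of 48–72 h use (s) nor its correlation with the 48 h total (r). Assume s = 0.5 to 2 mg and r = 0 to 0.7:

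SD72 = √(3² + s² + 2 × r × 3 × s)

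noncentrality = 1.7 / (SD72 × √(2/48))

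| s (mg) | r | SD72 (mg) | Noncentrality | Significant, two-sided t-test |
|---|---|---|---|---|
| 0.5 | 0 | √9.25 = 3.04 | 2.74 | 77% |
| 1 | 0.5 | √13 = 3.61 | 2.31 | 63% |
| 2 | 0.7 | √21.4 = 4.63 | 1.80 | 43% |

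**4. With the plan's unequal SDs.** A simulation used gamma-distributed 48 h use (4.1, SD 3 versus 2.4, SD 1.3), 48 per arm, and 48–72 h use that was identical in distribution in both arms and independent of earlier use (mean 0.5 to 1.5 mg, SD equal to the mean). The 72 h total was significant in about 87–96% of trials by t-test and about 74–85% by Wilcoxon. These figures depend on the independence assumption and the smaller SD in the active arm.

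**5. The interval test.** Under the same no-difference condition, a test of 48–72 h use alone is significant in about 5% of trials. Its detectable difference at 80% power is 2.80 × s × √(2/48): about 0.29, 0.57, 0.86 and 1.14 mg for s = 0.5, 1, 1.5 and 2 mg.

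**The case against.** A reader might infer that the trial cannot answer its question on duration. The documents do not support that. PCA use and pain scores by POD, opioid use by POD and time to first PCA dose are all collected, and none of them is a running total across days. Point estimates for each interval could even be obtained by subtracting the differences at 24, 48 and 72 h. What that subtraction does not supply is a confidence interval or test, or a prior statement that the interval is the evidence.

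Three further points have force:

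- **Loose wording.** The Secondary Aim says at 24 and 72 h, and the data form uses total requirements for single-day columns. Only the 48 h aim and the 72 h window in the Analysis Plan are clearly cumulative. That is a reason to define the windows, and the 72 h problem remains under the Analysis Plan's wording.
- **Near-tautology.** Step 3 assumes 1.7 mg and finds 1.7 mg again, and a significant 72 h total in that setting is not a false positive, because 72 h consumption truly differs. This is right. The percentages show how often the total would be open to misreading as day-3 benefit; they are not an inflated type I error.
- **No stated misuse.** Nowhere does the protocol say that a significant 72 h total will be taken as proof of day-3 relief. It expects the clearest difference at 48 h, and its success criterion is lower opioid consumption. This limits the seriousness of the point, but the goal of showing duration is still left without a designated analysis.

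**Conclusion.** This is a cheap improvement to the analysis plan. The stated goal includes duration, the named opioid outcomes accumulate, and no interval contrast is designated to address duration. The carry-over itself is exact arithmetic.

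Its size depends on assumptions. With 1.7 mg by 48 h, nothing further by 72 h and 48 per arm, the 72 h total is significant in about 43–77% of trials with SD 3 mg in both arms. The 87–96% figure needs unequal SDs and independent day-3 use and should not be quoted alone. The comparable figure for the interval itself is about 5%.

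The 0–48 h primary comparison is unaffected as a measure of total opioid use, and nothing here calls for a different sample size.

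**What to change.** Keep the 0–48 h total as the primary endpoint. Then revise section C (Secondary Aim), section E (Parameters Measured) and section G (Analysis Plan and Statistical Analysis Plan) as follows:

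1. Pre-specify opioid use in 0–24, 24–48 and 48–72 h, or by POD, each with the between-arm difference and 95% CI.
2. Define time zero and how the PACU and POD columns map to these windows, since calendar days need not match 24 h periods from the block or the end of surgery.
3. State that any claim of longer relief rests on the later intervals, supported by pain scores by POD, and that the cumulative 72 h total is descriptive.
4. Give the detectable difference for the interval contrasts under stated SDs.
5. Reconcile the catheter infusion length. Section D and the design summary give 48 h, whereas Treatment Regimen has the infusion running up to POD 3. Until these agree, the catheter arm's 48–72 h contrast cannot be interpreted.

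The cost is wording, a timing definition and a few tables. The two later intervals add 2 × 2 = 4 secondary contrasts against single shot, or 2 × 3 = 6 with all pairs. No new patients or visits are needed.

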All post-surgical patients are given a Dilaudid (or the equivalent dose of Morphine if not tolerated) IV PCA with every 10 minutes bolus function following surgery to be initiated immediately upon admission and transfer from the PACU to the floor. A clinician bolus of Dilaudid 0.5 mg every 30 minutes will be made available for additional pain control if needed.

Acetaminophen (Tylenol) will also be made available for treatment of post-operative pain on the floor.

Treatment Regimen

Patients assigned to the study group will randomly be assigned to one of the three arms described above. Patients in the catheter arm will receive a commercially available ON-Q® pain management system filled with 0.2% Ropivacaine. The ON-Q® system consists of an ON-Q® elastomeric infusion pump that will be connected to an end-orifice catheter. Patients in the catheter arm will receive a 20 ml bolus of Bupivacaine via Tuohy needle in the TAP space followed immediately by tunneling of a catheter into the TAP space under ultrasound guidance prior to extubation and complete emergence from general anesthesia. Said catheter will be left to infuse continuous local anesthetic site up to post-operative day 3. Patients in the two (2) single injection arms will similarly receive a bilateral injection of study local anesthetic (Exparel or Bupivacaine) 25-30ml per side in the TAP space prior to the conclusion of surgery under ultrasound guidance. Intra-operatively patients in all three study arms will receive IV fentanyl and IV Acetaminophen 1000mg unless drug allergy or intolerance to either medication.

Initial rescue IV pain medication will be made available similarly in all three study arms according to the institution's protocol for PACU breakthrough pain and will consist primarily of IV Dilaudid (or Morphine equivalent if patient does not tolerate Dilaudid). All post-surgical patients are given a Dilaudid (or Morphine if not tolerated) IV PCA with q10min bolus function following surgery to be initiated immediately upon admission and transfer from the PACU to the floor. A clinician bolus of Dilaudid 0.5 mg every 30 minutes (or Morphine equivalent) will be made available for additional pain control if needed. Tylenol will also be made available for treatment of post-operative pain on the floor.

E3.b Method for Assigning Subjects to Treatment Groups

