will be flushed with the Bupivacaine syringe. 2) The TAP space will be located using the Bupivacaine syringe under ultrasound guidance. 3) Once the TAP space, Exparel 133mg will be injected into the TAP space. 4.) After injection, the syringe will be exchanged for the Bupivacaine syringe and the residual Bupivacaine will be injected into the space (~20ml). Steps 2-4 will be repeated for the opposite side TAP block.

- 3) Continuous Catheter Arm: A total of 40 ml Bupivacaine 0.25% vials will be pre-drawn up via two 20 ml Syringes. The Bupivacaine 20ml syringe will be connected to IV tubing. The distal end of the IV connection will be maintained sterile and will be connected to the injection touhy needle. Procedure step 1) The entire setup will be flushed with the Bupivacaine syringe. 2) The TAP space will be located using the Bupivacaine syringe and ultrasound guidance. 3) Once in the TAP space, 5-10ml Bupivacaine 0.25% will be injected into the TAP space. The IV extension will then be disconnected from the touhy needle and a catheter will then be threaded via the touhy needle and into the TAP space. The proximal end of the catheter will then be connected to the distal end of the IV extension set and the residual Bupivacaine 0.25% from the 20ml syringe will then be injected thru the catheter. The catheter will then be secured and dressed via standard technique for catheter placement. Steps 2-4 will then be repeated for the opposite side TAP block. In the PACU, patients will receive a pre-filled ON-Q[®] system obtained through the hospital pharmaceutical department. The pre-filled ON-Q[®] system contains Ropivacaine 0.2% in a 700 ml container. The infusion pump will be set to run at a rate of 7 ml/hr. per side.

Breakthrough pain will be managed similarly in all three arms via Dilaudid IV PCA every 10 minutes with clinician bolus function of 0.5 mg every 30 minutes.

E3.d Subject Compliance Monitoring

The Principal Investigator will oversee compliance with study procedures.

E3.e Prior and Concomitant Therapy

N/A

E3.f Packaging/Labeling

N/A

E3.g Blinding of Study Drug

It will be impossible to blind the catheter group from practitioners and floor care nurses given the obvious appearance of the catheters. However, the floor care nursing and staff will be blinded between the single injection arms: Exparel and Ropivacaine. The

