Schedule of Measurements Template (add additional information as needed)

Anesthesiologist performing TAP BLOCK	Surgeon
Date of Surgery	Hospital Discharge Date
Procedure  Ventral hernia  Expl. Lap  Colon  Small Bowel  Anterior Resection  APR  Lower Anterior Resection  Prostate  TAH  HIPEC  Cyto-reductive Surgery  Ileostomy reversal  Robotic Assisted +/- Hand Assisted  Robotic (no incision)  L/S Assisted +/- Hand Assisted  L/S (no incision)  Other _____	 Continuous TAP with Ropiv 0.2%  Single Shot TAP  Exparel  0.25% Bupivacaine  Pre-incision  Post-incision Other: _____

PATIENT INFORMATION

Initials	Outpatient / SDA  Patient taking narcotics at home prior to surgery?  Yes  No	Inpatient (prior to Surgery)  PCA  IV narcotics  (skip if PCA) P.O. Narcotics  (skip if PCA)	
Age	Gender  M  F	Race  Cauc  Black (Non Hisp)  Hisp  Asian  Other	ASA
BMI	Smoking  Yes  No	Diabetes  Yes  No	
Incisional Dermatone Level Range: (Umb=T10)	Surgery Duration (minutes)	PACU Time until nurse gives report	

Outcomes	PACU	POD 0	POD 1	POD 2	POD 3
PCA		 Y  N	 Y  N	 Y  N	 Y  N
NARCOTICS					
MSO4 (mg) total requirements					
Dilaudid (mg) total requirements					
Fentanyl (mg) total requirements					
Anti-emetic Given (+/-)					
EVENTS					
Bowel Movement (+/-) (record 1 st day only)					

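### Time to first dose is listed under IV PCA use without a definition and, read as first PCA dose, cannot register opioid need in the PACU

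*Combined protocol and SAP*

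**What the plan says.** Item 2 of Parameters Measured (section E, Overview or Design Summary) reads "Days of IV PCA use: Time to 1st dose, total IV PCA requirements", followed by the post-operative days and other narcotics and adjuvants. Item 3 is a separate line, "PACU narcotic requirements". Neither item gives a time zero, says which dose is the first, or says what happens to a patient who takes none.

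The Treatment Regimen in section E says that the PCA is "to be initiated immediately upon admission and transfer from the PACU to the floor". Before that, rescue in all arms is available "according to the institution's protocol for PACU breakthrough pain and will consist primarily of IV Dilaudid", with morphine as the alternative.

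The Statistical Analysis Plan in section G has one general rule for continuous variables, a t-test or Wilcoxon rank-sum test. Missing Outcome Data says that missing values are left out of the analysis. The data form in section L has a yes/no PCA entry by day and narcotic totals by period, including a PACU column. As the form is reproduced, no field for a first-dose time is visible.

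**The concern.** The Study Abstract and the design overview both describe the "primary goal being to determine the effectiveness and duration of post-operative pain relief". Time to first opioid is a natural descriptor of duration, and readers of a trial report will take it as one. If it is recorded as first PCA dose, a patient whose relief failed soon after waking and who was rescued in the PACU can be recorded with a later first dose. The PACU narcotic total shows that such a patient was rescued, but not when.

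There is a second gap at the other end of the scale. Patients who never take a dose are those with the best relief. They have no time to enter, and a rule that excludes missing values could remove them from the comparison.

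**Working it through.** The documents give no figure for time to first dose, for PACU stay or for the share rescued in the PACU. There is therefore nothing to reproduce, and the check is mainly logical.

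**Step 1: what can be recorded.** Measure from end of surgery. Let T be the time of first opioid need, P the time of leaving the PACU and D the time of first PCA dose. The PCA starts at P, so D ≥ P for every patient.

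- Clock at end of surgery: the record is D, never less than P. If T < P, it overstates time to first need by D − T ≥ P − T > 0.
- Clock at PCA start: the record is D − P. It contains nothing about a need met before P.
- If T ≥ P and no PACU dose was given, D follows T, and the surgery clock gives the right answer.

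**Step 2: two patients (assumed values).** Both leave the PACU at P = 1.5 h.

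- Patient A needs opioid at T = 0.5 h, is rescued in the PACU, and first uses the PCA 0.5 h after leaving: D = 1.5 + 0.5 = 2.0 h.
- Patient B needs nothing until T = 2.0 h: D = 2.0 h.

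Both are recorded as 2.0 h on the surgery clock, or 2.0 − 1.5 = 0.5 h on the PCA clock. Their true times are 0.5 h and 2.0 h.

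**Step 3: how many patients this could touch (assumed values).** Take T lognormal with median m and log-SD 0.8, and P lognormal with median 1.5 h and log-SD 0.3, independent. The share with need in the PACU is

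Φ[(ln 1.5 − ln m) / √(0.8² + 0.3²)], where √0.73 = 0.854.

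The recorded median comes from a simulation of 400,000 patients on the surgery clock. First PCA dose is set at P + 0.5 h for patients rescued in the PACU and at T otherwise.

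| True median m (h) | Share needing opioid in PACU | Recorded median (h) |
|---|---|---|
| 0.5 | Φ(1.29) = 90% | 2.02 |
| 1 | Φ(0.47) = 68% | 2.11 |
| 2 | Φ(−0.34) = 37% | 2.46 |
| 6 | Φ(−1.62) = 5% | 6.00 |

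With early need, real differences are compressed: a true change from 0.5 to 1 h appears as 2.11 − 2.02 = 0.09 h. With late need the measure is close to correct.

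**Step 4: patients with no dose.** The general test rule needs a value for each patient. A Wilcoxon test could give never-dosed patients the longest rank, but the plan does not say so, and its missing-data rule points to leaving them out. Their number cannot be derived from the documents.

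**The case against.** The strongest reply is that the protocol lists this measure and does not define it. Item 2 goes on to other narcotics and adjuvants, so first PCA dose is the likelier reading but not a stated rule. That stands, and it makes the missing definition the core of the point. It is also fair that PACU opioid is available for breakthrough pain and not given to everyone, and that the PACU amount is collected, so a rescued patient can be identified. But an amount carries no time.

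Importance is limited too. The Primary Aim is total narcotic over 48 h, and duration is also covered by totals at 24, 48 and 72 h and by daily pain scores. The protocol expects the control block to last up to 24 h and the arms to differ most at 48 h, so an early first-dose time may separate them little, however it is defined.

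A reader might go further and infer bias in favour of the catheter arm, because E3.c says "In the PACU, patients will receive a pre-filled ON-Q" and only that arm has this step. The documents do not support this. They give no duration for the step and do not say that transfer waits for it. Even if it did add time, the effect would depend on the undefined clock. Under the Step 3 assumptions, with 0.5 h added to the catheter arm's stay and equal true relief, the spurious difference in medians is 0.49 h for early need on a surgery clock and about 0 for late need. On a floor-arrival clock it is 0 for early need and −0.5 h for late need.

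A reader might also infer that the measure mostly reflects length of PACU stay. That holds only if many patients need opioid early: under the same assumptions the rank correlation with PACU stay runs from 0.94 (m = 0.5 h) down to 0.02 (m = 6 h). Nor is this a case against time in PACU as an outcome, which the form records as "PACU Time until nurse gives report". A real delay there would be a consequence of the technique, and the study rationale counts procedural time and maintenance among the catheter's burdens.

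**Conclusion.** The point holds in limited form. Time to first dose lacks a time zero, a dose rule and a censoring rule. On its natural reading it cannot register opioid need in the PACU, whichever clock is used. That follows from the protocol's own text and needs no assumption beyond reading the item as first PCA dose.

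How much it distorts the measure is unknown. It grows with the share needing opioid in the PACU, and the 5% to 90% range shown is an illustration on assumed inputs. An arm-specific shift from the pump step is possible but not shown. The loss of never-dosed patients is a likely result of the general test and missing-data rules, again of unknown size.

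Severity is minor. The measure is not in the aims, the listed secondary outcomes or the named analyses, and the comparison of total narcotic use does not rest on it.

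**What to change.** In Parameters Measured, define the item as time from end of surgery to the first post-operative opioid dose by any route, PACU doses included. Add a field for that clock time to the data form in section L. In the Statistical Analysis Plan, state that it is analysed as a time-to-event outcome, for example with Kaplan-Meier curves and a log-rank test, censored at 72 h or at last observation if earlier. Patients who take no dose then stay in the comparison.

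Time to first PCA dose may be kept as a descriptive item on PCA use, labelled as such and with its starting clock stated.

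The cost is one extra clock time per patient from the medication record, plus a few lines of protocol and analysis-plan wording. No treatment or rescue procedure changes.
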